## **12. SAFETY ANALYSIS**

The Safety Population is defined as all enrolled patients who received any amount of study treatment will be utilized for all safety analyses.

In addition to the summary tables, safety data will also be presented in the individual patient listings.

The MTD will be assessed during the first cycle of treatment though toxicities observed during Cycle 2 and later cycles will be considered when determining the RP2D and the dose escalation scheme. Tumor response will be evaluated after Cycle 2 and every other cycle thereafter.

### **12.1 Treatment Emergent Adverse Events**

Treatment-emergent adverse events (TEAEs) are defined as all AEs that begin on or after the date of the first administration of study drug. Related AEs are those reported as possibly related, probably related, or related to study drug. The verbatim terms of the Treatment Emergent Adverse Events (TEAE) will be coded to preferred terms (PT) and system organ

classes (SOC) per MedDRA® (Medical Dictionary for Regulatory Activities) Version 21.0 (or later).

All reported AEs (including non-TEAEs) will be listed, documenting all information collected on the eCRF including verbatim term, MedDRA preferred term, MedDRA system organ class, start date, stop date, severity and relationship to study drug, action taken, and outcome.

The TEAEs will be graded by the Investigator in terms of:

- Severity graded 1-5 according to CTCAE v5.0:
  - 1=Mild, 2=Moderate, 3=Severe, 4= Life Threatening, 5=Fatal.
- Relation to study drug:
  - ‘Related’ includes events where the causality was reported as ‘Possibly Related’, or ‘Probably Related’, or ‘Definitely Related’, or where the relationship was not reported on the eCRF.
  - ‘Not Related’ includes events where the study drug causality was reported as ‘Unrelated’ or ‘Unlikely Related’ on the eCRF.

All TEAE summary tables will be presented with the number and percentages of patients in the Safety population. An overall summary of TEAEs will be tabulated by treatment regimen, relation to study treatment, and grade. In addition, TEAEs will be summarized by system organ class (SOC) and preferred term (PT).

Planned TEAE summary tables include:

- Overall Summary of Treatment-Emergent Adverse Events (Safety Population)
- Incidence of Treatment-Emergent Adverse Events by MedDRA System Organ Class and Preferred Term (Safety Population)
- Incidence of Treatment-Emergent Adverse Events by MedDRA System Organ Class, Preferred Term, and CTCAE Severity Grade (Safety Population)
- Incidence of Treatment-Emergent Grade 3, Grade 4, and Grade 5 Adverse Events by MedDRA System Organ Class and Preferred Term (Safety Population)
- Incidence of Treatment-Emergent Grade 3, Grade 4, and Grade 5 Adverse Events by MedDRA System Organ Class and Preferred Term and CTCAE Severity Grade (Safety Population)

- Incidence of Treatment-Emergent Adverse Events Judged Possibly, Probably or Definitely Related to the Study Drug Regimen by MedDRA System Organ Class and Preferred Term (Safety Population)
- Incidence of Treatment-Emergent Grade 3, Grade 4, and Grade 5 Adverse Events Judged Possibly, Probably or Definitely Related to the Study Drug Regimen by MedDRA System Organ Class and Preferred Term (Safety Population)

In the summary tables, patients may be counted under multiple system organ class (SOC) and preferred terms (PT), but for each SOC and PT category, patients are only counted once. If a patient has the same AE on multiple occasions, the highest severity grade (fatal > life threatening > severe > moderate > mild) or drug relationship (related > possibly related > not related) recorded for the event will be summarized.

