5.2.1.1 Cycle 1 – Day 1 (and as otherwise indicated)

- Patients receiving DEC (***during dose escalation***) and Alvocidib
 - Initiate TLS prophylaxis and supportive care measures according to each institution's standard of care
- Patients receiving AZA and Alvocidib
 - Administer pretreatment IV hydration prior to first AZA dose per institutional standards
 - Begin oral allopurinol daily from Days 1-14 of Cycle 1
 - Begin oral phosphate binder daily from Days 1-14 of Cycle 1 (see [Section 4.5.1.1.2](#))
 - Replace excessive fluid losses, including from diarrhea, unless otherwise clinically indicated (see [Section 4.5.1.2](#) and [Section 4.5.1.3](#))
- Record vital signs (temperature, heart rate, systolic and diastolic blood pressures) prior to first dose
- Obtain baseline signs and symptoms prior to first dose
- Collect blood for evaluation of laboratory parameters ([Appendix E](#)):
 - Hematology panel
 - Full serum chemistry panel
 - Tumor lysis labs required just prior to AZA dose in patients receiving AZA + alvocidib and 2 hours post AZA dose ([Appendix A-3](#))
 - Immediately assess potassium level at 2 hours post dosing for indications of tumor lysis syndrome
 - Tumor lysis labs to also be drawn on Days 2 and 3 prior to AZA doses during Cycle 1
- Collect peripheral blood for PD analyses on Days 1, 3 and 5 in patients receiving DEC or on Days 1, 3, 5, and 7 in patients receiving AZA ([Section 7.4](#), [Table 9](#) and [Table 10](#), respectively)

- Collect urine or serum sample for β -hCG pregnancy test for females of child-bearing potential if screening pregnancy test is greater than 72 hours prior to first dose
- Administer prophylactic antibiotics, antivirals, antifungals, antiemetics, antidiarrheals according to standard practices at each investigational site
- Administer DEC on Days 1-5 (***during dose escalation***) or AZA on 7-day or 5-2-2 schedule according to [Section 4.4.2.1](#)
- Assess for AEs
- Record only those medications (prescription, nonprescription, nutritional supplements) administered in conjunction with an AE.

**5.2.1.2 Cycle 1 – Day 8 (Patients receiving DEC + Alvocidib)
Cycle 1 – Day 10 (Patients receiving AZA + Alvocidib)**

- Perform an abbreviated physical examination (AE- or symptom-directed exam)
- Record vital signs (temperature, heart rate, systolic and diastolic blood pressures) 5-15 minutes prior to initiation of alvocidib following a 5-minute rest
- Assess ECOG PS ([Appendix B](#))

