8.4 ELICITING AND REPORTING ADVERSE EVENTS

All adverse events, regardless of severity, which occur during the study, will be documented in the study progress notes, and the "Adverse Event" case report form will be completed. This includes both serious and non-serious events. Adverse events occurring from the time of the first dose will be captured.

All adverse events noted by study staff or volunteered by study patients at any time will be recorded. The PI or a qualified designated staff physician will conduct clinical assessments of all patients at each scheduled clinic visit. In addition, patients will be queried about any adverse symptoms they have experienced since the previous study visit. In order to avoid bias in eliciting events, suggestive questioning of the patients shall not occur.

A laboratory abnormality will be reported on the "Adverse Event" case report form only if it is the main causative factor of an SAE, requires a therapeutic intervention, is the reason for a patient coming off study, or meets DLT criteria. Record the highest grade of the laboratory abnormality with start and stop dates associated with that grade. Laboratory values for hematology and serum chemistry parameters will be collected during the time the patient is on study to facilitate duration of worst CTCAE grade per cycle change-from-baseline analyses and overall worst CTCAE grade during the study. Any laboratory parameters assessed outside the per-protocol visits (ie, interim labs) will be recorded as 'Unscheduled Laboratory Assessments' in the database.

Adverse events will be reported and described in terms of intensity, seriousness and causality, based on the PI's judgment using protocol-defined definitions. Necessary counter measures will also be reported on the appropriate case report form used to collect concomitant medications.

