11. STATISTICAL CONSIDERATIONS

11.1 GENERAL CONSIDERATIONS

Protocol TPI-ALV-102 is a Phase 1b / 2, multicenter, open-label study in which Phase 1b will employ the 3+3 dose-escalation design, dose expansion at MTD/RP2D, and Phase 2 utilizing the Simon 2-stage minimax design [27].

Results of statistical analyses, descriptive statistics, and supporting listings will be presented by study phase (Phase 1b and Phase 2) and within alvocidib dose level. In addition, overall statistics will be calculated for Phase 1b patients across all alvocidib dose levels and for the total study population (ie, regardless of study phase).

Statistical analysis for all safety and efficacy parameters will be primarily descriptive in nature. Categorical variables will be summarized by frequency distributions (number and percentages of patients), continuous variables will be summarized by mean, standard deviation, median, minimum, maximum, and time-to-event variables will be summarized using Kaplan-Meier methods and figures for the estimated median time. No formal statistical hypothesis testing is planned; however, if exploratory analyses are conducted and confidence intervals (CIs) are provided for estimates, the 95% confidence intervals are consistent with a 2-sided 5% significance level. All analyses, summaries, and listings will be performed using SAS software (version 9.4 or higher).

A detailed methodology for summary and statistical analysis of the data collected in this study will be documented in a Statistical Analysis Plan (SAP) that will be finalized prior to database lock. The SAP may modify the data analysis plans outlined in the protocol; and if so, will be clearly documented in the SAP. Any major modifications of the study design or study endpoints and/or its analysis will also be reflected in a protocol amendment.

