11.10.1 Adverse Events

Adverse events will be classified using the MedDRA classification system version 20.0 or higher. The severity of the toxicities will be graded according to the NCI CTCAE v5.0.

In all summaries, emphasis will be placed on TEAEs, namely, those with initial onset or that worsen in severity after the first dose of alvocidib. Adverse events will be summarized by the frequency of patients experiencing TEAEs corresponding to body systems and MedDRA preferred term and by worst NCI CTCAE (v5.0) grade. Summaries will also be provided of treatment-related TEAEs, namely, those judged by the investigator to be related or likely related to alvocidib and/or combination regimens.

Adverse events resulting in discontinuation of alvocidib treatment or withdrawal from the study, Grade 3 or higher, serious adverse events, and deaths on-study will be tabulated.

All DLTs will be reported and the MTD and RP2D identified.

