## **16. STATISTICAL ANALYSIS CHANGES FROM THE PROTOCOL**

The analyses described are based on the final clinical study protocol ALV-102 Amendment 4 dated August 19, 2020. This SAP supersedes the statistical considerations identified in the protocol.

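### SAP 12.1 omits worsening from the protocol's TEAE definition, leaves the anchor drug unclear, and section 16 does not record the change

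*SAP*

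**What the plan says.** **Definitions.** Under SAP 12.1, TEAEs "are defined as all AEs that begin on or after the date of the first administration of study drug". Under protocol 11.10.1 they are "those with initial onset or that worsen in severity after the first dose of alvocidib". The SAP has no worsening limb and a different anchor.

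**Which text governs.** SAP sections 1 and 16 both settle this: "This SAP supersedes the statistical considerations identified in the protocol". Protocol 11.1 attaches a condition: "The SAP may modify the data analysis plans outlined in the protocol; and if so, will be clearly documented in the SAP". SAP section 16 cites the protocol amendment it is based on and names no individual change.

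**How events reach the database.** Protocol 8.4: "Adverse events occurring from the time of the first dose will be captured". For laboratory abnormalities only, it adds: "Record the highest grade of the laboratory abnormality with start and stop dates associated with that grade". Conditions present before dosing are handled separately; protocol 5.2.1.1 tells sites to "Obtain baseline signs and symptoms prior to first dose", and 5.1.2 asks for the same within the 72 hours before Day 1.

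**Outputs.** Every adverse event table planned in SAP 12.1 and every serious adverse event table in 12.2 is limited to treatment-emergent events. SAP 12.1 also lists all reported events, whether or not treatment-emergent. SAP 9.5.1 treats an event with a missing or partial date as treatment-emergent unless something contradicts that.

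**The concern.** The TEAE flag decides entry to all the adverse event and serious adverse event summary tables. No other table would show a worsening, because SAP 12.3 to 12.8 put laboratory tests, vital signs, ECG, ECOG status and physical examination in listings only. (SAP 3.7.1 still speaks of shift tables, a separate inconsistency.) Protocol 8.3 sends complications of marrow suppression to the adverse event form rather than to serious event reporting, and promises that the reports will summarize them. In this SAP only the TEAE tables can do that.

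Patients enter with cytopenias and whatever symptoms accompany them. If a complaint recorded before the anchor becomes severe after it, the protocol's rule tabulates it and the SAP's rule may not. A reader of the study report would not learn from section 16 that the rule had changed.

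**Working it through.** The plan states no figure to reproduce. The check sets the two rules side by side and traces each kind of record through them.

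**Step 1: the anchor.** Azacitidine or decitabine starts on Day 1. Alvocidib follows on Day 8 (after decitabine) or Day 10 (after azacitidine) (protocol 4.4.2). Protocol 5.1.2 puts the first dose of study drug on Day 1, and 4.4.1 speaks of study drugs in the plural. Protocol 9.1, however, calls alvocidib the investigational study drug and describes the other two as approved products. The SAP populations section does not settle it: where protocol 11.4 ties study treatment to alvocidib in parentheses, SAP section 6 leaves the parentheses out. Both readings of SAP 12.1 are therefore open.

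**Step 2: is the record counted as a TEAE?** Onset dates are complete except in row 7.

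| Row | Record | Protocol 11.10.1 | SAP, any study drug (Day 1) | SAP, alvocidib only (Day 8/10) |
|---|---|---|---|---|
| 1 | Onset after first alvocidib | Yes | Yes | Yes |
| 2 | Onset between Day 1 dosing and alvocidib, no later worsening | No | Yes | No |
| 3 | Onset between Day 1 dosing and alvocidib, worse after alvocidib, one record keeping its first onset date | Yes | Yes | No |
| 4 | Present before Day 1, worse after alvocidib, entered at the date of worsening | Yes | Yes | Yes |
| 5 | As row 4, but entered with its pre-Day 1 onset date | Yes | No | No |
| 6 | Laboratory abnormality with its highest grade after alvocidib, dated to that grade | Yes | Yes | Yes |
| 7 | Onset date missing or partial | No rule stated | Yes, unless contradicted | Yes, unless contradicted |

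**Step 3: reading the table.**
- Rows 3 and 5 are the possible losses. Row 5 is lost under either reading of study drug; row 3 only if study drug means alvocidib.
- Row 2 is a gain for the SAP if study drug includes decitabine and azacitidine.
- With complete dates and the Day 1 anchor, the SAP count is the protocol count minus row 5 plus row 2. With the alvocidib anchor it is the protocol count minus rows 3 and 5.
- The documents give no counts for rows 2, 3 or 5 and do not settle the anchor. The net direction is therefore undetermined.

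**Step 4: scale only.** The cohorts are 3, 3, 3, 4, 3 and 4 patients (SAP section 1), 20 in all. One patient moved in or out of a row changes the incidence by:
- cohort of 3: 1/3 = 33.3 percentage points
- cohort of 4: 1/4 = 25.0 points
- total: 1/20 = 5.0 points

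These are the weights of any single patient, not an estimate of the loss. SAP 12.1 counts a patient once per preferred term, so an excluded record changes an incidence only if the patient has no other qualifying record in that row.

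**The case against.** The strongest defence is that the capture rules do most of the work of the missing words. Adverse events are collected from the first dose, and earlier conditions go to baseline signs and symptoms or medical history. A condition that worsens on treatment and is then reported would normally carry an on-treatment start date and meet the SAP rule (row 4). Laboratory events are dated to their highest grade. Missing or partial dates default to treatment-emergent. Events outside the TEAE definition remain in the listings, which matter a good deal in a synoptic report on 20 patients. DLTs are defined by grade, relation and duration (protocol 4.5.3, SAP 8.6), not by TEAE status. Exclusions 3 and 8 also keep out the more severe infections and bleeding at entry.

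Most of this stands, and it makes the loss less likely, but it does not close the gap:
- The SAP itself provides for reported events that are not TEAEs.
- The dating rule in protocol 8.4 covers laboratory abnormalities only. Nothing says how to date a worsened symptom, so a site may enter the date it first appeared. The annotated case report form cited in SAP section 1 might contain such a rule, but it is not among the documents.
- The default for missing dates does not reach a complete date before the anchor.
- Capture from first dose is what brings row 3 records into the database, and the alvocidib reading then removes them from the tables.

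**Conclusion.** Three things are certain from the text: the worsening limb is missing, the anchor is ambiguous, and section 16 does not disclose the change that protocol 11.1 says must be documented. The consequence is conditional. A worsened event leaves the adverse event and serious adverse event tables only if its recorded onset is complete and precedes the anchor, and if the worsening stays on that same record.

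Two stronger conclusions are tempting, and the documents support neither. A reader might infer that pre-existing conditions which worsen on treatment disappear from all safety output. They do not: most would be entered with an on-treatment date, all reported events are listed, and DLT assessment does not use the TEAE flag. A reader might also infer that the SAP undercounts toxicity in one direction. With a Day 1 anchor, the SAP adds onsets between Day 1 dosing and alvocidib that the protocol leaves out, so the net effect could go either way.

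The number of affected events is unknown. The point is still worth correcting, because the stated rule can give different tables from the protocol's, columns of 3 or 4 patients are sensitive to one record, and the edit is small.

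**What to change.** Change the SAP only; the protocol allows the SAP to modify its analysis plan, and the study is closed.

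1. In SAP 12.1, define a TEAE as an adverse event with onset, or worsening in severity, on or after the first dose of any study drug (decitabine, azacitidine or alvocidib). With complete dates, this counts rows 1 to 6 above.
2. State that a post-dose worsening of a pre-existing condition has its onset at the date of worsening. Base this on recorded severity, because the protocol does not say that baseline signs and symptoms are CTCAE-graded.
3. In SAP section 16, record both differences from protocol 11.10.1: the anchor, and the dating of worsening.

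The cost is a few sentences and a review of adverse event records whose onset precedes the anchor. If the database is already locked, SAP section 1 provides for an addendum and a note in the study report.

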## **12.2 Serious Adverse Events**

Serious adverse events will be obtained from the AE dataset where any of the Seriousness Criteria of 1-6 is checked (note: AESAE criteria 7 = NOT serious).

Planned Serious TEAE summary tables include:

- Incidence of Serious Treatment-Emergent Adverse Events by MedDRA System Organ Class and Preferred Term (Safety Population)
- Incidence of Serious Treatment-Emergent Adverse Events Judged Possibly, Probably or Definitely Related to the Study Drug Regimen by MedDRA System Organ Class and Preferred Term (Safety Population)
- Treatment-Emergent Adverse Events in the Standardized MedDRA Query for Tumor Lysis Syndrome Judged Possibly, Probably or Definitely Related to the Study Drug Regimen by MedDRA Preferred Term (Safety Population)

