2.6 JUSTIFICATION FOR STUDY TREATMENT PLAN

About 30% of patients diagnosed with MDS will progress to AML. Patients with IPSS-R intermediate and above MDS have an increased risk of developing AML and may be treated with the same chemotherapy regimens used in patients with AML.

Two alvocidib dosing schedules (ie, bolus and hybrid dosing) have been evaluated in eight clinical trials in patients with AML (Table 1). While both regimens of ACM have shown substantial activity in patients with AML, the hybrid regimen will be used in this study. Clinical data from a randomized study that compared the two dosing regimens suggest that the hybrid schedule tends to produce a higher remission rate (62% versus 74%) in poor-risk, newly diagnosed AML patients [23]. A high CR rate (39%) has also been documented with the hybrid regimen in relapsed and refractory AML patients (and 92% CR among relapsed-only patients) [21]. In addition, the safety profile of the two regimens appears similar, though there may be a trend to lower early mortality with the hybrid regimen. In these two studies, the incidence of Tumor Lysis Syndrome (TLS) was 9%, and treatment-related mortality was 8% and 9%, respectively.

Alvocidib is a potent inhibitor of CDK9 and downregulates CDK9-driven transcription of super enhancer-regulated genes, such as c-Myc and MCL-1. Primary pharmacology of alvocidib is related to potent inhibition of CDK9 which disrupt super enhancer-driven expression of MCL-1 as this plays a central role in the super enhancer complex. The ability of alvocidib to alter the expression of MCL-1 may provide a novel approach to targeting MCL-1-dependent malignancies such as MDS or multiple myeloma. Apoptosis following alvocidib is rapid and not linked to cell cycle arrest [25].

In the clinic, three-day dosing of alvocidib resulted in an average reduction of circulating blasts of greater than 75% [19]. A functional assay has been developed to identify patients with a malignancy dependent on MCL-1 which involves adding NOXA peptide or a NOXA mimetic peptide (eg, T-MS1) to patient samples and measuring induction of apoptosis. The readout is percentage of cells entering apoptosis. In MDS patients, the assay is being planned to be run on peripheral blood as well as standard bone marrow aspirates on diagnostic bone marrow samples. This functional assay is scalable and has a quick turnaround (24-48 hours).

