4.5.1.1.3 Risk of TLS with Alvocidib and Guidelines for Management

TLS management during treatment with alvocidib was implemented in previous studies, which included medical prophylaxis for hyperuricemia, as well as aggressive monitoring and management of hyperkalemia and other biochemical laboratory abnormalities. Rapid development of hyperkalemia has been of particular concern in earlier studies with the hybrid dosing regimen of alvocidib. While these guidelines are not necessarily consistent with specific standard recommendations for the treatment of TLS, they are recommended based on previous experience with the treatment of patients with the hybrid dosing regimen of alvocidib. These measures resulted in a lower incidence of TLS without adverse outcomes.

For this reason, Investigators are encouraged to follow the recommended guidelines below but may follow your own institution's protocols in determining the best treatment for your patients.

- If potassium levels are increasing to >4.0 mEq/L, patients should receive a 30 gm dose of sodium polystyrene sulfonate, unless there are other likely causes of hyperkalemia other than TLS or contraindication to its use.
- If potassium levels rise to >5.0 mEq/L, in addition to the 30-gm dose of sodium polystyrene sulfonate, patients should also receive 10 units of IV rapid-acting insulin and 25 gm (1 ampule) of IV dextrose 50%, unless there are other likely causes of hyperkalemia other than TLS or contraindication to its use. Investigators are strongly encouraged to consider patient hospitalization for inpatient monitoring and follow up.
- If potassium levels rise to >5.5 mEq/L, patients should be considered for emergent intermittent or continuous dialysis.
- Calcium supplementation should only be given for symptomatic hypocalcemia in this setting to avoid renal precipitation of calcium phosphate crystals.
- Patients who develop clinical evidence of cytokine release syndrome or who have hyperkalemia requiring dialysis will receive immediate steroid therapy with an equivalent of at least 20 mg of IV dexamethasone.

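### The only TLS-specific table in the SAP is limited to events judged related and laid out by preferred term, so no planned table title gives the all-causality number of patients with any TLS-query event

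*SAP*

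**What the plan says.** SAP 12.2 lists three tables under the line "Planned Serious TEAE summary tables include". The third is the TLS table, covering events in the "Standardized MedDRA Query for Tumor Lysis Syndrome Judged Possibly, Probably or Definitely Related to the Study Drug Regimen by MedDRA Preferred Term". Its title does not contain the word serious, although the list it belongs to does.

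SAP 12.1 plans tables without any relationship filter, among them "Incidence of Treatment-Emergent Adverse Events by MedDRA System Organ Class and Preferred Term (Safety Population") and "Incidence of Treatment-Emergent Adverse Events by MedDRA System Organ Class, Preferred Term, and CTCAE Severity Grade (Safety Population"), plus Grade 3 to 5 tables. SAP 12.2 adds "Incidence of Serious Treatment-Emergent Adverse Events by MedDRA System Organ Class and Preferred Term (Safety Population"). All of these report patients, as counts and percentages. On counting, SAP 12.1 says that "patients may be counted under multiple system organ class (SOC) and preferred terms (PT"), with each patient counted once within a given class or term. No counting rule is given for a query. The same section treats possibly, probably and definitely related as related, and also any event whose relationship was not recorded. It promises a listing of every adverse event with its relationship.

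On TLS itself, protocol 4.5.1.1.3 says "Rapid development of hyperkalemia has been of particular concern in earlier studies with the hybrid dosing regimen of alvocidib". Protocol 2.6, on two earlier AML studies, states that "the incidence of Tumor Lysis Syndrome (TLS) was 9"%.

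**The concern.** TLS has its own prophylaxis, laboratory schedule and management guidance in the protocol. A reader of the study report will ask how many patients had a TLS-type event, overall and by cohort. The cohort split matters because prophylaxis differed: institutional practice after decitabine (protocol 4.5.1.1.1; Cohorts 1 to 4) and a protocol-specified scheme after azacitidine (4.5.1.1.2; Cohorts 5 and 6).

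The one table built for that question first passes each event through the investigator's causality judgement, in an open-label, single-arm study with no control group against which to check it. It then splits the result by preferred term. The SAP does not treat its other event groups this way. All TEAEs, Grade 3 to 5 TEAEs and serious TEAEs each get an all-causality table as well as a related-only one. The TLS query gets only the related-only one, and no reason is given.

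**Working it through.** The documents state no design figure on this point, so there is none to reproduce. The check is of what each planned output can yield.

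| Planned output | Relationship filter | What it counts | Distinct patients with any TLS-query event, all causes? |
|---|---|---|---|
| All TEAEs by class and term, also by grade (SAP 12.1) | None | Patients per class and per term | No; single terms only |
| Grade 3 to 5 TEAEs (12.1) | None, plus a related-only version | Patients per class and per term | No |
| Serious TEAEs (12.2) | None, plus a related-only version | Patients per class and per term | No |
| TLS query (12.2) | Related only | By preferred term | No |
| Adverse event listing (12.1) | None | Events, with relationship | Only by hand count |
| Laboratory data (12.3) | Not applicable | Values in listings | No |

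**Why term rows do not give patients.** If the query terms have patient counts c1, c2, ..., the number of distinct patients lies between max(c) and the smaller of sum(c) and N. With invented counts of 3, 2 and 1 and N = 20, the range is max(3, 2, 1) = 3 to 3 + 2 + 1 = 6 patients, or 15% to 30%. The class rows do not help, because they count patients with any event in the class, whether or not it belongs to the query.

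**What the filter removes.** Let d be the number of patients all of whose TLS-query events are called unrelated or unlikely. Then:

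- All-causality patients minus related-only patients = d, with d ≥ 0.
- Difference in the total rate = 100 × d / 20 = 5d percentage points.
- Within a cohort, one such patient is 100 / 3 = 33 points (N = 3) or 100 / 4 = 25 points (N = 4). Cohort sizes in SAP 8.1 are 3, 3, 3, 4, 3 and 4, which sum to 20: 13 after decitabine and 7 after azacitidine.

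The documents give no basis for a value of d.

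**Context only.** Protocol 2.6 and Table 4 report earlier TLS rates from 9% to 15/47 = 32%. Applied to 20 patients, these give 20 × 0.09 = 1.8 to 20 × 15/47 = 6.4 patients. At 9% the chance of at least one is 1 − 0.91^20 = 0.85. These rates come from AML studies of other regimens. They suggest the table may well not be empty, but say nothing about d.

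**Laboratory route.** SAP 12.3 gives laboratory data in listings only, although protocol 11.10.2 foresees shift tables by CTCAE grade. Under protocol 8.4 a laboratory abnormality becomes an adverse event only in set circumstances, such as causing an SAE, needing treatment or meeting DLT criteria. No laboratory summary therefore stands in for the missing count.

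**The case against.** The strongest reply is that little is hidden. A reader might infer that the number of patients with TLS is never reported free of attribution. The documents do not support that: a patient coded to the tumor lysis syndrome preferred term appears in the unfiltered tables, by cohort, whatever the investigator thought of causality. With 20 patients, the grouped count can also be taken from the listing. This stands. What is missing is the grouped all-causality count as a planned summary.

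Second, SAP 8.4 refers to table shells that are not in the text reviewed, so the TLS table may already open with an any-event row. This stands in part. The point rests on titles, and a shell could supply the row; but the relationship filter is in the title itself.

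Third, the filter can be defended as a choice for specificity. Protocol 4.5.1.1.3 recognizes hyperkalemia with causes other than TLS, and an all-causality query could count such events. This stands as a cost of the change, and so it cannot be said that the filtered rate is biased downward by a known amount. The rules in SAP 12.1 also soften the filter, since possible and unrecorded relationships count as related and the strongest relationship is kept for repeats of the same event.

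Fourth, the study closed early, reporting is descriptive and no decision turns on this table. That limits the importance of the point but does not answer it.

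**Conclusion.** The point holds as a gap in one safety summary: no planned table title yields the all-causality number of distinct patients with at least one TLS-query event. Each patient whose query events are all called unrelated or unlikely is 5 points of the total. How many there would be is unknown. This assumes that the TLS table follows the related-event definition in SAP 12.1 and that all 20 enrolled patients are in the denominator, as the SAP 8.1 column headers show.

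Two further inferences go beyond the documents. One is that TLS is the main alvocidib harm. The protocol calls it a particular concern but ranks nothing; Table 4 labels diarrhea the DLT in the monotherapy study (7/24, 29%) and shows neutropenic fever or infection in 14/24 (58%) there. The other is that the filtered figure would fail to match unfiltered earlier rates of 9% to 32%. The documents do not say how attribution was handled in those studies, and Table 4, although headed as serious events of Grade 3 or above, describes its 26% entry as mild.

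There is also a separate ambiguity: because the table sits in the list of serious-event tables, it is unclear whether non-serious TLS events count.

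The change is worth making because it is cheap and completes a reported safety figure. No trial conclusion depends on it.

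**What to change.** In SAP 12.2, before database lock:

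- Retitle the TLS-query table to cover all TEAEs in the query regardless of relationship.
- Add a first row for the number and percentage of patients with at least one TLS-query event, by cohort and in total, each patient counted once.
- Keep the related events as a sub-row or second column, so that the narrower reading stays visible.
- State that non-serious events are included, or move the table to SAP 12.1.

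The cost is one changed shell and its program, using adverse event data already due to be coded in MedDRA. The downside is that the all-causality count may include some electrolyte or creatinine events with other causes; the related-only sub-row lets a reader see how much rests on them. Nothing in TLS prophylaxis, monitoring or management would change.
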